APPENDIX V:

Subject ID: _____

Date: / / _____

Appendix V:

EpiPen Auto-Injector Demonstration Check-Off

Subject ID: _____

Date: / / _____

Investigator: Please initial next to each procedure as they are properly demonstrated.

Date	Investigator Initial	Procedures
		Correctly prepared the EpiPen or EpiPen Jr Auto-Injector for injection by: 
 • removing the auto-injector from the clear carrier tube
		
 • removing the blue safety release by pulling straight up without bending or twisting it
		Correctly demonstrated proper administration of EpiPen or EpiPen Jr Auto-Injector by: 
 • holding the auto-injector with orange tip near the outer thigh
		
 • firmly pushing the orange tip against the outer thigh until it “clicks”
		
 • kept the auto-injector firmly pushed against the thigh at a 90° angle (perpendicular) to the thigh.
		
 • firmly held the auto-injector against the thigh for approximately 10 seconds to complete drug delivery
		Correctly finalize the injection process by: 
 • removing the auto-injector from the thigh
		
 • massaging the injection area for 10 seconds
		
 • verbalized that they will call 9-1-1 immediately after for further medical attention

Caregiver Signature: _____ Date: ___/___/____

Investigator Signature: _____ Date: ___/___/____

Appendix VI: Peanut Oral Immunotherapy – Safety Checklist

Subject ID: _____ **Date:** ___/___/____

Please initial each line and sign/date at the bottom.

_____ I acknowledge that Caregiver understands the safety risks and implications of this study.

_____ Caregiver received training and understand how to use an Epinephrine injector.

_____ Caregiver received training and understands the signs and symptoms of an allergic reaction.

_____ Caregiver received training and understands when to give Benadryl, when to use an Epinephrine injector, and when to call 9-1-1.

_____ Caregiver understands the need to have their unexpired Epinephrine injector with them at all times.

_____ Caregiver/ understands that if Epinephrine injector is not with them during a research related appointment, then that appointment will be canceled and rescheduled.

_____ Caregiver understands that they will need to come to Texas Children’s Hospital every two weeks for the first year of the study, then every 6 months for the last two years of the study to receive their daily peanut doses.

_____ Caregiver understands that they must notify the research team of any allergic reactions, even mild cases, on the day the reaction occurs.

_____ Caregiver understands that they must call 9-1-1 for severe reactions and to obtain further medication attention.

_____ Caregiver understands that they will need to come to Texas Children’s Hospital the next day if a reaction occurs at home.

_____ Caregiver understands that his/her child will need supervision 2 hours after taking their daily peanut dose at home.

_____ Caregiver understands that his/her child cannot go to school within 2 hours of eating the peanut flour and cannot go to bed within 2 hours of eating the peanut flour.

_____ Caregiver received a contact list of phone and pager numbers from research team and I know who to call if my child experiences an allergic reaction.

_____ Caregiver understand that the peanut flour needs to be stored in a refrigerator with the container lids tightly closed.

_____ Caregiver understand that if his/her child misses 3-4 doses of peanut flour, they will have to come to Texas Children's Hospital to receive their next scheduled dose.

Investigator or designee Signature: _____

Date: / / _____

Appendix VII

Subject ID: _____

Date: / / _____

Peanut Equivalent Dosing Guide

Warning: It is your responsibility to ensure the product is safe for your child to eat.

- **ALWAYS** read labels on all foods
- Ingredients and protein amount can change without warning at any time
- These products may contain allergens and may not be safe for everyone
- M&M’s and Reese’s products contain milk and may contain tree nuts
- Be cautious about consuming candies manufactured outside the US
- Call the manufacturing company if there are any doubts about the product containing other allergens

Peanut Product	Peanut Protein (gram) /serving	Maintenance Dose (3900mg peanut protein)	Alternative Dose (if maintaining below 3900mg)
Creamy Peanut Butter *Peter Pan or Reese’s Creamy Peanut Butter*	8 grams=2 Tablespoons	1 Tablespoon	1300 mg =1 teaspoon 325mg=0.25 teaspoon
JIF Peanut Powder	8 grams=3 Tablespoons	1.5 Tablespoons	
PB2 Powdered Peanut Butter (Bell Plantation)	5 grams=2 Tablespoons	1.5 Tablespoons	1300 mg= 1.5 teaspoon 300 mg = 3/8ths of a teaspoon
Dry Roasted Peanuts	0.175 grams=1 peanut	22 peanuts	1300 mg = 7 and ½ peanuts

			350 mg = 2 peanuts
Peanut M&M's	0.15 grams=1 piece	26 pieces	1300 mg = 8 and 2/3 pieces 300 mg=2 pieces
Reese's Pieces Candy	0.078 grams=1 piece	50 pieces	1300 mg = 16 and 2/3 pieces 312 mg = 4 pieces
Reese's Peanut Butter Cups Miniatures	0.8 grams=1 miniature cup	~5 miniature cups	1300 mg = 1 and 5/8 th cups 300 mg = 3/8 th cup
Other approved alternative:			

1. The peanut equivalent dose may vary depending on the maintenance dose. The table is based on a maintenance dose of 3900mg.
2. You are able to choose any of the above foods to use for daily dosing.
3. Ensure the peanut protein amount is the same prior to purchasing product.
4. You should continue to follow the "Instructions for Daily Home Doses" as used for peanut flour dosing.

Parent Signature: _____ Date: __ / / _____

Investigator Signature: _____ Date: / / _____

Appendix VIII

Peanut Equivalent Instructions for Daily Home Doses

Subject ID: _____ Date: / / _____

Important: We require that you please carry with you 2 epinephrine auto-injector devices at all times and must demonstrate to the investigators the correct use of the epinephrine auto-injector. Failure to consistently carry an epinephrine auto-injector constitutes grounds for termination from the study. If you do not have an epinephrine auto-injector on your person, your appointment(s) will be rescheduled.

- Take one dose per day, preferably at the same time every day. Prior to taking the dose, you must eat a snack high in carbohydrate and fat (example: bagel, chips) then eat the peanut equivalent based on the “Peanut Equivalent Dosing Guide”.
- After eating the peanut equivalent, your child must be with a supervising adult for the next 1-2 hours (depending on provider’s instructions) so they can monitor for any possible reaction. Your child cannot go to school and cannot go to bed within the observation period. The provider may have the option of decreasing the observation period to 1 hour after 30 days of tolerating the peanut equivalent. Your child may eat and go to school after 1 hour. Your child should continue to avoid physical activity, hot showers, and going to bed within 2 hours of taking the dose.
- Travel
 - International Traveling
 - May consider international traveling once the subject is stable on maintenance for 6 months
 - Try to keep the dosing time period the same as in the USA. Keep the dosing time the same as your place of origin (i.e. dose time in the USA 4pm, then take the dose at 4pm final destination time). Up to 48 hours of dose could be missed
 - No dose should be taken during travel on the plane. Dosing may resume once you arrive at your final destination
 - Domestic Traveling within the continental U.S.
 - Take dose at the same time as place of origin (i.e. dose time in Houston 4pm, then take the dose at 4pm final destination)
 - No traveling on cruise ships

- Please ensure that the peanut equivalent food is not a food that your child is allergic to. Also, be sure to read the label on the food.
- Fill out symptom diary every day and record any symptoms occurring within the observation period of taking the daily dose.

Symptoms to look for:
Mild Symptoms (itching, mild flushing, sneezing, nasal congestion, eye itching, swelling of lips, hives/swelling in one or two areas of the body, nausea)
Moderate to Severe Symptoms (hives/swelling all over the body, shortness of breath, cough, chest tightness, vomiting, abdominal pain, feeling of tightness around the throat, feeling faint, skin turning blue, and breathing with loud, squeaky sounds)

- Please use the Allergic Reaction Treatment Plan as a guide during an allergic reaction.
- Call and inform the research team of any reaction (even mild cases) and make an appointment to see the research team for the following day.
- Please call 9-1-1 for severe reactions (example: confusion, loss of consciousness/non-responsive, collapse, incontinence, bluish skin, feeling faint).

If a daily dose is missed:
• Up to 2 days, continue doses as scheduled.
• 3-4 days after missed dose; repeat previous doses but this dose will be given at Texas Children’s Hospital.
• More than 4 days after missed dose, you/your child will return to Texas Children’s Hospital for a desensitization challenge procedure.

Parent Signature: _____ Date: __/ / _____

Investigator Signature: _____ Date: / / _____

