The CAGT is a Good Manufacturing Practice (GMP) compliant facility (See Letter of Authorization) and is accredited by the Foundation for the Accreditation of Cellular Therapy (FACT), the College of American Pathologists (CAP) and is CLIA registered. The protein doses will be monitored and dispensed by the CAGT GMP Facility.

The drug would be stored in the cold room (2-8°C) within the clean room area restricted to CAGT GMP Facility Staff. It is on continuous temperature monitoring via our Isensix system. In the case of an alarm staff is informed via pager system. Alarms and monitoring data are also full backed up by Isensix in San Diego. This drug will be stored in a dedicated facility away from other allergens and will be handled in a separate room on a separate air handling systems.

The pre-measured soufflé cups will be transported by a clinical research staff member within Texas Children's Hospital controlled environment.

The peanut flour will be used within the manufacturer's expiry date and our center will follow all instructions provided by the manufacturer.

One dose of peanut flour is taken per day. Prior to taking the dose the subject must eat a snack high in carbohydrate and fat such as a bagel or chips and then eat the peanut flour mixed into liquid or another food such as apple sauce or ice cream.

The vehicle food for each subject will be a food, to which the subject is not allergic. The subject will need to eat the peanut flour at approximately the same time every day. After eating the peanut flour the subject will need to be with a supervising adult for the next 2 hours so they can monitor for any possible reaction. The subject cannot go to school within 2 hours of eating the

peanut flour and cannot go to bed within 2 hours of eating the peanut flour. After 1 month, if there are no adverse events with the maintenance dose or highest dose tolerated, the provider will have the option of decreasing the observation period to 1 hour with no physical activity to occur for 1 hour.

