dose (Table 4). The first dose of the peanut equivalent will be given in the hospital setting. The family will be instructed on how to administer peanut equivalent dose. The subject will continue to follow the “Instructions for Daily Home Doses” as used for peanut flour dosing. This will be considered “Month 0”. The participant will remain on this dose for 24 months and follow-up visits will occur every 6 months. The subject will continue to follow the peanut flour dosing guidelines. A food challenge will be performed within 1 month of the “Month 0” visit.

Table 4. Peanut Equivalent Dose

Peanut Product	Peanut Protein (gram) /serving	Maintenance Dose (3900mg peanut protein)	Alternative Dose (if maintaining below 3900mg)
Creamy Peanut Butter *Peter Pan or Reese’s Creamy Peanut Butter*	8 grams=2 Tablespoons	1 Tablespoon	1300 mg =1 teaspoon 325mg=0.25 teaspoon
JIF Peanut Powder	8 grams=3 Tablespoons	1.5 Tablespoons	
PB2 Powdered Peanut Butter (Bell Plantation)	5 grams=2 Tablespoons	1.5 Tablespoons	1300 mg= 1.5 teaspoon 300 mg = 3/8ths of a teaspoon
Dry Roasted Peanuts	0.175 grams=1 peanut	22 peanuts	1300 mg = 7 and ½ peanuts 350 mg = 2 peanuts
Peanut M&M’s	0.15 grams=1 piece	26 pieces	1300 mg = 8 and 2/3 pieces 300 mg=2 pieces
Reese’s Pieces Candy	0.078 grams=1 piece	50 pieces	1300 mg = 16 and 2/3 pieces 312 mg = 4 pieces
Reese’s Peanut Butter Cups Miniatures	0.8 grams=1 miniature cup	~5 miniature cups	1300 mg = 1 and 5/8 th cups 300 mg = 3/8 th cup

Other approved alternative:			
-----------------------------	--	--	--

- If the subject experiences no adverse events with the maintenance dose or highest dose tolerated after 1 month, the provider will have the option of decreasing the observation period at home to 1 hour. The subject will need to avoid any form of physical activity 2 hours after ingestion.
- Peak Flow: Peak flow measures will be accepted with results >90% of predicted.
- Amount of blood to be drawn: After maximum tolerated dose is achieved at approximately 1 year (drawn at Visit 30- Month 0 DBPCFC) and every 6 months afterwards, we will draw up to 4-6 tablespoons of blood (based on the subject's weight) for peanut-specific IgE, IgG, and IgG4, cellular immune studies and basophil histamine release assays until the end of the protocol.
- Allergy Skin Prick Tests (PST): Endpoint dilution skin testing to peanut will be done at month 0 and month 12 visits.

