Appendix III: Instructions for Daily Home Doses

Subject ID: _____

Date: / / _____

Important: We require that you please carry with you 2 epinephrine auto-injector devices at all times and must demonstrate to the investigators the correct use of the epinephrine auto-injector. Failure to consistently carry an epinephrine auto-injector constitutes grounds for termination from the study. If you do not have an epinephrine auto-injector on your person, your appointment(s) will be rescheduled.

- Take one dose per day, preferably at the same time every day. Prior to taking the dose, you must eat a snack high in carbohydrate and fat (example: bagel, chips) then eat the peanut flour mixed in a small amount of liquid (example: less than 1 tablespoon (15 ml) of water, apple juice etc.) or mixed into another food (example: less than one half of a cup (8 tablespoons) of apple sauce, ice cream). Liquid or semi-solid foods can be mixed with the dose to facilitate consumption.

After eating the flour, your child must be with a supervising adult for the next 2 hours so they can monitor for any possible reaction. Your child cannot go to school, go to bed, or take hot showers within 2 hours of eating the peanut flour. No strenuous physical activity during the observation period.

- Travel
 - No international traveling is allowed
 - Domestic Traveling within the continental U.S.
 - Take dose at the same time as place of origin (i.e. dose time in Houston 4pm, then take the dose at 4pm final destination)
 - No traveling on cruise ships
- Please ensure that the vehicle food that the peanut flour is mixed with is not food that your child is allergic to.
- Record any symptoms occurring within 2 hours of taking the daily dose.

Symptoms to look for:
Mild Symptoms (itching, mild flushing, sneezing, nasal congestion, eye itching, swelling of lips, hives/swelling in one or two areas of the body, nausea)
Moderate to Severe Symptoms (hives/swelling all over the body, shortness of breath, cough, chest tightness, vomiting, abdominal pain, feeling of tightness around the throat, feeling faint, skin

turning blue, and breathing with loud, squeaky sounds)

- Please use the Allergic Reaction Treatment Plan as a guide during an allergic reaction.
- Call and inform the research team of any reaction (even mild cases) and make an appointment to see the research team for the following day.

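### Appendix VIII ties the maintenance diary window to a provider-set observation period, while section 6.5 and Appendix VII keep families on the flour sheet's fixed 2 hours

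*Combined protocol and SAP*

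**What the plan says.** Two family instruction sheets set a diary window.

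- **Appendix III** (peanut flour): "Record any symptoms occurring within 2 hours of taking the daily dose".
- **Appendix VIII** (peanut equivalent): "Fill out symptom diary every day and record any symptoms occurring within the observation period of taking the daily dose". On the same sheet, supervision reads "your child must be with a supervising adult for the next 1-2 hours", depending on the provider, and "The provider may have the option of decreasing the observation period to 1 hour after 30 days of tolerating the peanut equivalent".

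Two other places tell families on the peanut equivalent which instructions to use, and both name the flour sheet.

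- **Section 6.5**: "The subject will continue to follow the “Instructions for Daily Home Doses” as used for peanut flour dosing".
- **Appendix VII**, note 4: "You should continue to follow the 'Instructions for Daily Home Doses' as used for peanut flour dosing".

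Sections 6.2 and 6.5 also allow a 1-hour observation period, on a condition worded differently from Appendix VIII. Section 6.2 reads "After 1 month, if there are no adverse events with the maintenance dose or highest dose tolerated, the provider will have the option" of a shorter period, and 6.5 has the same condition. Neither section mentions the diary.

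Section 7 and section 8.1.3 call for daily diaries without giving a window. Section 9.2.1 names daily symptoms as part of the measurement of the primary objective, also without a window. The primary objective (2.1.1) describes treatment as 50 weeks of escalation and 104 weeks of maintenance.

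**The concern.** In build-up the diary window is a constant. In Appendix VIII it becomes whatever the provider sets for supervision. A safety precaution that may reasonably be relaxed as a child does well then also decides which symptoms are written down.

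Three things could follow for a daily-symptom summary. The window could be shorter in maintenance than in build-up. It could differ between participants in the same phase. It would also shorten in participants who tolerate dosing, so the length of the window would be related to the outcome being recorded.

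The study plans 15 participants and has no placebo arm. Daily-symptom results would naturally be read descriptively, within participants and across phases. A fall in recorded symptoms during maintenance could then be partly a fall in recording.

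**Working it through.** The plan gives no figure to reproduce. The check is a comparison of the texts, followed by a note on what the size would depend on.

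**Step 1. Which window applies in each phase.**

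| Source | Applies to | Diary window |
|---|---|---|
| Appendix III | flour dosing | 2 hours, fixed |
| Section 6.5; Appendix VII note 4 | peanut equivalent | by reference to the flour sheet: 2 hours |
| Appendix VIII | peanut equivalent | the observation period: 1 to 2 hours, possibly 1 hour after 30 days |
| Sections 7, 8.1.3, 9.2.1 | whole study | none stated |

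A maintenance family is therefore pointed to two sheets with different recording rules, and no passage ranks them.

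**Step 2. What follows under each reading.**

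- Every family follows Appendix III: 2 hours throughout, with no difference between phases or participants.
- Families follow Appendix VIII and the provider keeps 2 hours: again no difference.
- Families follow Appendix VIII and the provider shortens: 1 hour after the first month for those participants, 2 hours for the rest.

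Only the third case has a consequence, and its frequency depends on provider choices that the documents do not predict.

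**Step 3. Whether shortening is related to the outcome.** Appendix VIII makes it conditional on 30 days of tolerating the dose. Sections 6.2 and 6.5 make it conditional on a month without adverse events. The conditions differ, but under either one the participants with quieter records are those who can be moved to the shorter window.

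**Step 4. What the size would depend on.** Let f be the share of symptomatic doses within 0 to 2 hours whose onset falls in the second hour. The documents do not give f; the values below are assumptions. Assume also a constant reaction rate, exact adherence to the window, a 2-hour window in month 1 and a 1-hour window for the other 23 of 24 maintenance months. Relative to a family with the same reactions and a 2-hour window, the recorded share is

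(1 + 23 × (1 − f)) / 24

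- f = 5%: (1 + 21.85) / 24 = 0.95
- f = 10%: (1 + 20.7) / 24 = 0.90
- f = 20%: (1 + 18.4) / 24 = 0.81
- f = 50%: (1 + 11.5) / 24 = 0.52

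If the provider does not shorten, or the family follows Appendix III, the ratio is 1. The spread shows that f drives the result. It is not an estimate of bias in this trial.

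**The case against.** The strongest reply is that the conflict is only apparent. Appendix VIII is specific to the peanut equivalent by its title and carries parent and investigator signature lines. Section 6.5 itself adds the 1-hour option after pointing to the flour instructions, which suggests that the specific sheet updates the general one. This is the natural reading, but it remains an inference, because 6.5 and Appendix VII expressly name the flour instructions. Accepting it does not remove the problem: the maintenance window then does depend on the provider.

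A second reply is that late reactions are captured elsewhere. Appendices VI and VIII require families to report any reaction, even a mild one. Section 12.5 puts all adverse events on case report forms. Diaries are reviewed at visits, and the diary comments field asks for further symptoms. This largely stands for safety reporting. A reader might infer that second-hour reactions would be lost to the study; the documents do not support that. What they leave open is whether those reports are added to the daily-symptom measure.

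Third, the link to the primary objective is limited. Section 9.2.1 names baseline and 50 weeks or one year as its time points, and 6.5 places approximately one year at the Month 0 challenge. On that reading the option to shorten opens essentially after the one-year assessment. Section 9.2.1 also defines no per-dose symptom rate and no test between phases. This stands and confines the point to a descriptive summary that includes maintenance days.

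Finally, most of the printed diary form is not in the available text and may carry its own window. That cannot be held against the plan. If it does, it would still have to agree with both sheets.

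**Conclusion.** The point holds as a minor inconsistency in measurement. If Appendix VIII is followed and providers use the option, the diary window can be shorter in maintenance than in build-up, can differ between participants, and shortens in those who tolerate dosing. A descriptive daily-symptom summary covering maintenance could then look quieter partly because of the window.

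The size cannot be derived. It ranges upward from no effect and depends on three things the documents do not give: which sheet families use, how often providers shorten, and the share of symptoms starting in the second hour.

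Two stronger readings are not supported. A reader might infer that the primary efficacy result is biased, but the proportion tolerating the challenge and the change in tolerated dose come from supervised food challenges and do not use the diary. A reader might also infer bias in the viral-symptom analysis of 9.2.3. That analysis counts symptomatic doses, but nothing in the documents says that second-hour symptoms relate to viral illness, so no bias can be claimed.

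**What to change.** Reconcile section 6.5, Appendix III, Appendix VII and Appendix VIII so that one fixed diary recording window, the 2 hours already used in Appendix III, applies in both phases and is worded separately from the supervision period. State in 9.2.1 that daily-symptom summaries use that window, and whether call-in and adverse event reports are counted in them. Check that the printed diary form agrees.

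This changes recording only; the supervision rule is untouched. The differing conditions for shortening observation in 6.2, 6.5 and Appendix VIII must also be reconciled, and that is for the sponsor to settle.

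The cost is one sentence in Appendix VIII, one or two in 9.2.1, and matching cross-references. The downside is that Appendix VIII allows an early return to school ("Your child may eat and go to school after 1 hour"). Second-hour symptoms may then rest on the child's later report rather than on an adult's observation, so comparability between phases improves without becoming complete.
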